MBRP-SA Development. The primary adaptation for MBRP-SA will be to tailor some the session content and discussions to smoking cessation and alcohol use. These changes will be primarily guided by the existing literature (e.g., studies on mindfulness-based treatments for smoking cessation) and the experience/knowledge of the investigative team. It should be noted that MBRP already addresses some of the primary underlying mechanisms of smoking cessation and reduced alcohol use (e.g., managing negative affect and craving) and that the extant literature indicates that key behavior modification constructs (e.g., self-efficacy) are impacted by mindfulness.^{45,50,67,76} Therefore, we will not modify the core components of MBRP, but instead supplement the existing protocol with content unique to smoking and alcohol use.

Content Modifications. Content modifications listed here fall into 3 categories: smoking-specific, alcohol-specific, and co-use. Given MBRP has already demonstrated efficacy for reduced alcohol use, most of these modifications focus on smoking and co-use content. Modifications are based on the existing literature, ability of content to address underlying behavior-change mechanisms (e.g., motivation) and Co-I [name] experience developing and testing a mindfulness-based cessation intervention.⁵⁸ **SMOKING-SPECIFIC: Quit date.** Research regarding smoking cessation indicates that motivation can be enhanced by setting a specific quit date.¹⁴² Therefore, MBRP-SA will set the smoking quit date at Session 5, which is supported by existing mindfulness-based cessation treatments (e.g., ⁵⁸). This permits time for individuals to develop their mindfulness practice (Sessions 1-4) while still providing ongoing support for 3 weeks after the quit day. **Losing a friend.** Many smokers report that smoking a cigarette represents a type of "friendship" and that quitting smoking is like losing a close friend.¹⁴³⁻¹⁴⁵ MBRP-SA will acknowledge and process this type of cognition in Session 3. **Diet and Weight Gain.** Many individuals endorse motivation to continue smoking for weight control purposes,¹⁴⁴ and therefore we will include information on this topic in Session 3. **Nicotine Patch.** Current guidelines for smoking cessation indicate that when provided with a combination of nicotine replacement therapy and counseling, chances of success are greatest.¹⁴² Thus, participants will be

[figure not shown]

Figure 3. Treatment Development Flow

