provided with nicotine patches at the end of Session 4, with the intention to begin using them at Session 5. Psychoeducation about patch use will occur at Session 4. Mindful Smoking is a mindfulness activity that brings awareness to the act of smoking a cigarette. An introduction to this will occur at the end of Session 2, and the actual practice will be conducted right before the beginning of Session 3 group. Participants will be encouraged to continue mindful smoking until their quit day at Session 5. **ALCOHOL-SPECIFIC:** Reduced alcohol use. Alcohol use will be monitored at each treatment session. A discussion of goals related to reduced drinking will begin at Session 1 and continue through Session 5. Participants will be encouraged to set realistic drinking goals for themselves, which is consistent with a harm reduction approach to alcohol use and fits within the framework of social determination theory.^{146,147} Participants will be encouraged to implement drinking goals at Session 5 (to coincide with the smoking quit date), although many people may have already decreased use. At the orientation session, participants will be provided with a handout with psychoeducational information on alcohol use, and they will be encouraged to use this when deciding what their alcohol use goal will be. **CO-USE:** Psychoeducation on the health impacts of cigarette and alcohol use. Consistent with recommendations,¹⁴² participants will be provided with psychoeducation information on the impact of cigarette and alcohol use on their health at Session 1. Information on the benefits of quitting smoking and reducing drinking (e.g., breathing becomes easier, decrease risk of cancer development) will also be discussed and provided. Relationship between smoking and drinking. Given common underlying mechanisms of the co-use of alcohol and smoking exist (e.g., cue-induced craving, positive and negative reinforcement),¹¹⁻¹⁶ discussions related to the inter-connected relationship among smoking and alcohol use will be conducted. This discussion will also include a focus on previous attempts to change either or both behaviors by participants. We will also highlight that continued alcohol use may serve as a trigger for relapse. Discussions regarding whether complete abstinence is the best option for some participants will be conducted. We believe this added content will aid participants in making the best decision regarding their own co-use. These discussions will occur at Session 2.

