Table 5. Measureable Benchmarks

Area of Interest	Description of Outcome to be Evaluated	Measure and/or Expected Outcome
Acceptability	Participant Satisfaction	Client Satisfaction Questionnaire ¹⁵⁸ (satisfaction of ≥80%)
	Intention to continue to use skills learned from the treatments	Questionnaire developed for this study
	Perceived appropriateness of the treatments for smoking and alcohol use	Questionnaire developed for this study
Demand	Accrual rates for study	For recruitment, the cost of each participant will be ≤\$100
	Completed sessions	≥40% of participants will complete all 8 sessions; ≥60% will complete between 4 and 7 sessions*
	Homework Completion	For MBRP-SA, participants will engage in mindfulness homework at a minimum of 3.5 days per week*
Implementation/ Practicality	Screening/eligibility for study	Record number of call attempts for each participant and reasons for ineligibility
	Recruitment	Recruit 8 eligible participants per month; 60% of recruitment will be completed by the end of year 2
	Retention	Retain 80% through end of treatment, 70% through follow-up
	Questionnaire completion	For sessions attended, 90% of questionnaires will be completed

Note. * based on data from Bowen et al., 2014; Vidrine et al., 2016; Witkiewitz et al., 2014^{64,66,107}

Aim 3.

The primary goal of Aim 3 is to collect and examine descriptive data on proximal variables associated with smoking abstinence and reduced drinking (e.g., negative affect, craving), as well as distal variables (smoking abstinence, heavy alcohol use) from Study 2. Aim 3 will be underpowered to test for any main effects of treatment on clinical outcomes. Nonetheless collecting these data will contribute to our assessment of feasibility and will provide guidance as we determine the sample size for a full-scale efficacy trial.

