To ensure participant confidentiality, no unique identifiers will be recorded into the dataset to be analyzed. Data will be collected via REDCap. The entered and reviewed data will be transferred monthly to a SPSS database.¹⁷⁴

Sample Size. Randomizing 64 participants to MBRP-SA and CBT will provide sufficient data for assessing feasibility of the RCT, based on existing recommendations in the literature for sample size estimates in feasibility studies.^{175,176} A full set of statistical analyses focusing on treatment differences will be performed as part of the feasibility assessment. However, the sample size will not be sufficient for detecting treatment differences for anything less than large effect sizes (e.g., Cohen's $d \geq .72$) for simple, two-group comparisons of a continuous variable with $\alpha=.05$, power $\geq .80$, and a two-tailed test. Binary variables assessed under the same testing conditions would require an $OR \geq 5.95$.

Data Analysis Overview. Analyses will be conducted with SPSS and SAS version 9.4¹⁷⁴ and Mplus Version 7.¹⁷⁷ Descriptive statistics of demographics, smoking history, and alcohol history variables will be calculated and group comparisons will be performed. Descriptive statistics of all study measures (i.e., proximal and distal measures of alcohol use and smoking) will be calculated. Although underpowered to detect small- or medium sized sex differences, all analyses will examine sex as a covariate. Furthermore, analyses will include treatment group (i.e., each subset of participants who are treated with MBRP-SA or CBT together) when the intraclass correlation coefficient is > 0.10 .

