A similar approach to analysis will be taken for the primary outcomes (the distal measures). TLFB will be used to derive a measure of heavy alcohol use and the 7-day point prevalence will be created for smoking abstinence at five targeted 1-week periods prior to a session: start of treatment (week -4), quit date (week 0), end of treatment (week +3), and two follow-ups (week +8 and week +16). Descriptive statistics will be presented in figures. GEE with an AR(1) working correlation matrix ($r=.60$) will be used to assess the effects of treatment, time (-4, 0, +3, +8, +16), and their interaction on the primary outcome measures. Means, percentages, and 95% confidence intervals will provide useful guidance as we determine sample sizes for a full-scale RCT. There is not adequate power to detect small- to medium-sized treatment group differences given the sample size. However, we would interpret any within-subject decreases in the number of heavy drinking days from pre- to post-treatment and/or any within-subject increases in smoking abstinence as evidence that the MBRP-SA intervention may be beneficial for these two problematic health behaviors. Given the small sample size, these changes are not likely to be significant. However, sample means and standard deviations will provide valuable data for

estimating sample size in a large-scale RCT. Changes in craving, self-efficacy, and general use of alcohol and smoking will also be examined as proximal outcomes that will also inform the development of a large-scale trial.

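### One hedged Aim 3 sentence counts any within-subject improvement as evidence for MBRP-SA, with no threshold and no comparator, so it says little about MBRP-SA itself (minor, interpretation only)

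*Combined protocol and SAP*

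**What the plan says.** The sentence is in section 2, part G (Data Management and Statistical Considerations for Study 2), in the Aim 3 paragraph on the distal outcomes. It opens "we would interpret any within-subject decreases in the number of heavy drinking days from pre- to post-treatment and/or any", and its second half reads "any within-subject increases in smoking abstinence as evidence that the MBRP-SA intervention may be beneficial". The next sentence concedes that significance is not expected.

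The surrounding text limits what hangs on this:

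- The same paragraph plans GEE models that "will be used to assess the effects of treatment, time (-4, 0, +3, +8, +16), and their interaction on the primary outcome measures".
- It also says "Means, percentages, and 95% confidence intervals will provide useful guidance as we determine sample sizes for a full-scale RCT".
- The Aim 3 introduction states that "Aim 3 will be underpowered to test for any main effects of treatment on clinical outcomes".
- The Sample Size paragraph says "A full set of statistical analyses focusing on treatment differences will be performed as part of the feasibility assessment".
- Feasibility is judged on the Table 5 benchmarks, which do not include this sentence.

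**The concern.** The sentence moves from description to evidence without naming a size of change, a precision requirement or a comparator. Three features of the design make its smoking half easy to meet and hard to attribute.

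- **Starting point.** Section 1.1 requires current daily smoking for entry, so abstinence in the week before week -4 is about 0% and can only rise.
- **Shared treatment.** Section 1.1 requires everyone to be motivated to quit and to cut down drinking. The Treatment Overview gives patches to all participants, and the two programmes have equal contact time. The plan itself says that "when provided with a combination of nicotine replacement therapy and counseling, chances of success are greatest", and both arms get both. Some quitting is therefore expected in each arm whatever MBRP-SA adds.
- **No untreated arm.** Even if MBRP-SA is read as the whole package with patches, a pre-to-post rise has nothing to be set against.

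The word and/or then lets either outcome suffice. What is at stake is a favourable statement about MBRP-SA that the data would support with almost no information specific to MBRP-SA.

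**Working it through.** **The plan's own figures.** The plan gives no operating characteristic for this sentence. Its nearest figures, in the Sample Size paragraph, are d ≥ 0.72 and OR ≥ 5.95 at two-sided α = 0.05 and power 0.80. With 64 randomised in balanced blocks there are 32 per arm. For the mean difference, 0.72 × √(32/2) − 1.96 = 0.92, so power is 0.821 by the normal approximation (0.809 by the noncentral t). For the odds ratio, a 10% control rate gives odds 0.111 × 5.95 = 0.661, a rate of 39.8% and power 0.802. Both figures reproduce with 32 per arm. The plan does not state that control rate, and 60% v 90% fits equally well, so it supplies no quit rate.

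**Inputs for the smoking half.**

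- Assessed in the MBRP-SA arm: 32 if all are seen. Table 5's 80% and 70% retention give 0.80 × 32 = 25.6 (26) and 0.70 × 32 = 22.4 (22).
- Baseline abstinence: 0, from section 1.1.
- Quit rate q in the arm: assumed at 2%, 5% and 10%.
- Any increase: at least one abstainer at one assessment. This holds whether the wording is read per participant or per arm.

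**Independent participants.** P = 1 − (1 − q)^n. For example, 1 − 0.95^22 = 0.676 and 1 − 0.90^32 = 0.966.

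| Assessed | q = 2% | q = 5% | q = 10% |
|---|---|---|---|
| 32 | 48% | 81% | 97% |
| 26 | 41% | 74% | 94% |
| 22 | 36% | 68% | 90% |

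**Clustering by treatment group.** Treatment is given in groups of 8-10, so a beta-binomial allowance is reasonable. With ICC ρ, put s = (1 − ρ)/ρ and b = (1 − q)s. A group of m has no abstainer with probability ∏(b + i)/(s + i), i = 0 to m − 1. The arm's probability is 1 minus the product over groups. I take 32 as four groups of 8, and 22 as groups of 6, 6, 5 and 5.

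| ICC (assumed) | 22, q = 5% | 22, q = 10% | 32, q = 5% | 32, q = 10% |
|---|---|---|---|---|
| 0.05 | 64% | 87% | 75% | 94% |
| 0.10 | 60% | 85% | 70% | 92% |

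**Direction of the other simplifications.** Counting several assessments would raise these figures. The sentence does not say that change is judged in the MBRP-SA arm only. Pooling the arms (44 to 64 assessed) gives 90% to 99.9% at 5-10% under independence. The drinking half can only add to the chance that the condition is met. I put no number on the combined condition, because that needs a chance rate for a fall in drinking and the dependence between the outcomes. The plan treats the two behaviours as linked ("discussions related to the inter-connected relationship among smoking and alcohol use will be conducted").

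**The case against.** The strongest reply is that the sentence says only that MBRP-SA may do some good. CBT is an active, established treatment, so an MBRP-SA arm that matches or trails CBT could still be beneficial. That stands. A reader might infer that the sentence wrongly declares a win whenever MBRP-SA does no better than CBT, or is worse. The documents do not support that reading, because superiority over CBT is never claimed. The percentages above are therefore not error rates. They show how often the condition is met, and at 5% or 10% some people really have quit. The defect is one of attribution.

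It is also fair that Aim 3 is openly descriptive and underpowered, that the wording is hedged, and that treatment-by-time models and 95% CIs are planned. A reader might infer that the between-arm analysis is missing or that progression turns on this sentence. Neither is so. What remains is that the evidence statement is not tied to those analyses.

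Finally, the quit rates are assumed. At 2% the smoking half is met in fewer than half of trials, so it would be too strong to say that it is met in most trials without naming the rate.

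**Conclusion.** The point holds and is minor. As written, a single abstainer lets the team cite evidence for MBRP-SA. Under independence that occurs in 36-48%, 68-81% and 90-97% of trials at assumed quit rates of 2%, 5% and 10% with 22 to 32 assessed. Allowing for group clustering, the 5-10% range is about 64-94% at ICC 0.05 and 60-92% at ICC 0.10. These figures rest on zero baseline abstinence, one assessment and the MBRP-SA arm alone. With shared patches, shared motivation, equal contact time and no untreated arm, a within-arm rise cannot be credited to MBRP-SA. The GEE, the confidence intervals and the Table 5 benchmarks are unaffected, so the harm is confined to interpretation.

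**What to change.** Replace the sentence with:

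> Within-arm changes in heavy drinking days and smoking abstinence will be reported for both arms as description and not as evidence of benefit of MBRP-SA. Any statement about MBRP-SA relative to CBT will rest on the estimated between-arm difference with its 95% CI, read as estimation only; for smoking, the cotinine-verified difference is at week +16, and differences at weeks +3 and +8 will be labelled self-report only. Similarity to CBT will not be read as lack of benefit.

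The self-report label is needed because the Smoking Abstinence paragraph defines the outcome with saliva cotinine, while that paragraph and Table 4 provide for one cotinine test, at the 16-week follow-up. The GEE stays as it is.

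No new data or model is needed, because percentages with 95% CIs are already promised. The smoking difference adds one line of output at each of three time points. The price is a less favourable-sounding conclusion and wide intervals. At an illustrative 10% v 20%, the half-width 1.96 × √(0.09/n + 0.16/n) is 17 percentage points with 32 per arm, 19 with 26 and 21 with 22, before any allowance for clustering.

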3. REGULATORY AND REPORTING REQUIREMENTS

3.1 Institutional Review Board

No subject is to be enrolled on this protocol until the Center's Institution Review Board has approved it.

3.2 Monitoring

Monitoring plan development for this project is commensurate with the risks proposed by the project. Monitoring will be ongoing by the principal investigator (PI-[name]), and the Institutional Review Boards (IRB) of Advarra. Overall, the plan for monitoring includes: 1) Monitoring the progress of the study; 2) Assuring compliance with the requirements for reporting adverse events that may occur during the study; and 3) assuring data accuracy and protocol compliance. For all study protocols, the PI is responsible for the reporting of adverse events to the IRB.

[name] will oversee the implementation of the study and daily monitoring. This will include weekly meetings to discuss any issues related to the progression of the project and factors that may affect the outcome, including a review of data quality and security, recruitment, and retention. Adverse events will also be discussed. A brief report will be created and submitted annually for the study record and submitted to the Chesapeake IRB. For any problems that may arise, [name] will consult with the co-investigators to discuss how to best proceed.

3.3 Informed Consent

The investigators and the research associated are responsible for obtaining consent by the participants. The consent process will be conducted remotely, and a waiver of written consent will be requested from the IRB to allow us to obtain verbal consent. Informed consent will be obtained over the phone prior to entry of any participant.

3.4 Investigator Study Files

Research records for patients on this study are the responsibility of the investigator. They will be available for review by the sponsors of the trial, health care personnel involved in this study, the IRB, DHHS, and the FDA.

Sources of Materials

Data collected from participants for research purposes include a saliva testing for Cotinine (a nicotine metabolite) and self-report measures and interview data that collect demographic, medical history, psychiatric symptoms, smoking-related information, alcohol-use information, and questions about personality traits and current affective and cognitive states. Data will be collected electronically via REDCap. The treatment sessions for the MBRP-SA group involve mindfulness (meditation) practice that is tailored to smoking cessation and reducing alcohol use. The treatment sessions for the CBT group involve coping and reappraisal skill training that is tailored to smoking cessation and reducing alcohol use. Participants will be asked about the feasibility and acceptability of the treatments, in addition to monitoring their homework practice each week.

Potential Risks

Minimal risks are anticipated for this study. Data including self-report, interview (psychological and medical), and biological samples (e.g., saliva) involve risk of breaches in confidentiality. Although everyone will be asked to keep the information shared during the group sessions confidential and to maintain anonymity outside of sessions, a breach of confidentiality is always possible. Participants will always be given the option to refuse to answer any questions on the measures that may be distressing. Successful abstinence may cause irritability, anxiety, general distress and difficulty concentrating. The nicotine patch that participants will wear beginning on the quit date will be the appropriate dose for their level of smoking, and the patch should aid in the management of withdrawal symptoms. The nicotine patch and smoking cessation counseling have been shown to be safe and effective for smokers attempting to quit. However, side effects to the patch may occur and include skin irritation/ rash, nausea, dizziness, dry mouth, diarrhea, nervousness, headache, vivid dreams or sleep disturbances, irritability, and irregular heartbeat.

Protections Against Risks

We believe that this study poses minimal risks. Potential side effects from the nicotine patch will be closely monitored by study staff and the PI. Participants will be told of potential allergic reactions and side effects in response to the patch and nicotine side effects, and also told that they are free to remove the patch at any point in time. Should participants feel any possible side effects, they will be advised to discontinue the patch, and also told that they can call the PI and study staff. Counseling will be provided by clinicians who have received ample training regarding ethical principles of counseling. Emergency procedures will be in place should any psychiatric emergency arise during the screening and/or treatment processes. Although this is likely to be very rare, all study personnel and counselors will be trained in these procedures. Should a person drop-out of treatment early, community referrals for smoking, alcohol use, and mental health services will be provided. To ensure that any data (e.g., psychological, medical, personal) collected from this study remains confidential, hardcopy and electronic storage of data will be identified by participant number, so that data will not be directly associative with names. Association between participant names and numbers will not be kept in the same location as the data. Electronic files will be protected by password access, and hard copies will remain in a locked cabinet when not in use. Saliva samples will be discarded and have no identifying information after analyses.

Any electronic data will be stored on internal drives and in password-protected files without participant identifiers. Storage of any paper files will be kept in locked filing cabinets. Only study personnel will have access to these files.

